Clinical Trial Protocol: BPS-314d-MR-PAH-302

Study Title:	A multicenter, double-blind, randomized, placebo-controlled, Phase 3 study to assess the efficacy and safety of oral BPS-314 d -MR added-on to treprostinil, inhaled (Tyvaso®) in subjects with pulmonary arterial hypertension
Study Number:	BPS-314 d -MR-PAH-302
Study Phase:	3
Product Name:	Beraprost Sodium 314d Modified Release
IND Number:	111,729
Indication:	Treatment of Pulmonary Arterial Hypertension
Investigators:	Multicenter
Sponsor:	Lung Biotechnology Inc.
Sponsor Contact:	
Medical Monitor:	

	Date
Original Protocol:	16 April 2013
Amendment 1:	17 December 2013
Amendment 2	15 October 2014

GCP Statement: This study will be conducted in compliance with the protocol, Good Clinical Practice (GCP) and applicable regulatory requirements.

Confidentiality Statement The concepts and information contained herein are confidential and proprietary and shall not be disclosed in whole or part without the express written consent of Lung Biotechnology Inc. © 2014 Lung Biotechnology Inc.

LIST OF CONTACTS

Study Sponsor:	Lung Biotechnology Inc. [name] United States [contact] [contact]
Sponsor Contact:	
Medical Monitor:	
SAE Reporting:	

SYNOPSIS

Sponsor: Lung Biotechnology Inc.

Name of Investigational Product: Beraprost Sodium 314d Modified Release

Name of Active Ingredient: Beraprost Sodium 314*d* (BPS-314*d*)

Study Title:

A multicenter, double-blind, randomized, placebo-controlled, Phase 3 study to assess the efficacy and safety of oral BPS-314*d*-MR added-on to treprostinil, inhaled (Tyvaso®) in subjects with pulmonary arterial hypertension

Study Number: BPS-314*d*-MR-PAH-302

Study Phase: 3

Primary Objective:

The primary objective of this study is to compare the effect of BPS-314*d*-MR versus placebo added to treprostinil, inhaled (Tyvaso®) on the composite endpoint of time-to-clinical-worsening (TtCW), defined as the time from randomization to the first of any of the following clinical worsening events:

- Death (all causes)
- Hospitalization due to worsening PAH defined as:
 - Non-elective hospitalization lasting at least 24 hours in duration caused by clinical conditions directly related to PAH and/or right heart failure and requiring intensification of treatment; or
 - Lung or heart / lung transplantation; or
 - Atrial septostomy
- Initiation of a parenteral (infusion or sub-cutaneous) prostacyclin, directly related to worsening PAH (transient use [≤7 days] for non-PAH related illness allowable)
- Disease progression (all criteria required):
 - A decrease in six minute walk distance (6MWD) of at least 15% from Baseline (defined as the average of the two 6MWTs performed on sequential days of the Baseline Visit), or being too ill to walk as a consequence of PAH progression, confirmed by six-minute walk tests (6MWT) performed at 2 consecutive visits
 - Worsening of PAH symptoms, which must include either:
 - An increase in WHO Functional Class or
 - Worsening symptoms of right heart failure
- Unsatisfactory long-term clinical response (all criteria below required):
 - Receiving randomized treatment for at least 24 weeks
 - A decrease of at least 15% from Baseline (defined as the average of the two Baseline Visit 6MWTs) in 6MWD, or too ill to walk, directly related to PAH progression, at Week 24 and beyond; at 2 consecutive visits, and
 - Sustained WHO Functional Class III or IV symptoms for at least 24 weeks.

Secondary Objectives:

- To compare the effect of BPS-314*d*-MR versus placebo added to treprostinil, inhaled (Tyvaso®) on the composite endpoint of time-to-clinical-failure (TtCF), defined as the time from randomization to the first of any of the following events:
 - Meets primary endpoint definition of clinical worsening, as confirmed by EAC; or
 - Receiving randomized treatment for at least 24 weeks and has:
 - Lack of sustained improvement from Baseline WHO Functional Class: defined by two consecutive visits of no sustained improvement from Baseline WHO FC, visits may be scheduled or unscheduled; and
 - Lack of sustained improvement from Baseline 6MWD (average at Baseline): defined by two consecutive visits of no sustained improvement from Baseline 6MWD (≤ 0 meters or too ill to walk, directly related to PAH), visits may be scheduled or unscheduled.
- To compare the effects of BPS-314*d*-MR to placebo on changes from baseline to each scheduled study visit, as applicable, for the following measures:
 - 6MWD
 - Borg Dyspnea Score
 - WHO Functional Class
 - NT-pro-BNP levels
- To evaluate the safety of BPS-314*d*-MR based on adverse events, clinical laboratory parameters, electrocardiogram (ECG) findings, physical examination and vital signs.

Exploratory Objectives:

•		
-		

Study Design:

A multicenter, double-blind, randomized, placebo-controlled, Phase 3 study to assess the efficacy and safety of oral BPS-314*d*-MR added-on to treprostinil, inhaled (Tyvaso®) in subjects with pulmonary arterial hypertension.

Patients who consent to the study will be assessed at the Screening and Baseline Visits to determine eligibility for the study. After the Screening Visit, subjects who consent to the study and are determined to be eligible but are not currently taking inhaled treprostinil will enter a run-in period on inhaled treprostinil to achieve 90 days of experience to ensure drug tolerability before being randomized. During the run-in period, subjects will be prescribed inhaled treprostinil by the Investigator and will receive the Tyvaso® inhalation device and inhaled treprostinil, and training in accordance with specialty pharmacy and the standard procedures of the clinical site. Subjects who consent to the study and are currently taking inhaled treprostinil at the Screening Visit should be randomized into the study as soon as eligibility criteria have been met. Subjects who meet eligibility criteria and who have been treated with inhaled treprostinil for at least 90 days, with 30 or more of the 90 days at a stable dose, at the time of the Baseline Visit

will be randomized into the study using a centralized randomization system, stratified by use of inhaled treprostinil, to either active or placebo study drug. Subjects who are initially ineligible for this study may be reassessed for eligibility following consultation with the Sponsor. Following randomization, the subject, study site staff, the Sponsor and the Event Adjudication Committee (EAC) will all be blinded to the treatment group assignment.

Following the Baseline Visit, subjects will return to the study site at Week 4, Week 8, Week 12 (first Quarterly Visit) and for Quarterly Visits thereafter. During these study visits, subjects will undergo all scheduled efficacy and safety assessments as defined by the protocol and the Schedule of Events (Appendix 1). Between scheduled study visits, the subject will be contacted by phone to assess for possible clinical worsening events and to record any newly occurring or changes to adverse events or concomitant medications. Phone contact should be made weekly (except during study visit weeks) between Baseline and Week 12 (first Quarterly Visit), then monthly between Quarterly Visits through the end of study participation.

An optional hemodynamic assessment will be offered to subjects at selected study sites providing those sites agree to participate in the hemodynamic study and are approved by the Sponsor. Hemodynamic measurements which will be measured/calculated are heart rate, pulmonary arterial pressure (systolic, diastolic and mean), systemic arterial pressure (systolic, diastolic and mean), right atrial pressure, pulmonary capillary wedge pressure, mixed venous oxygen saturation, system arterial oxygen saturation, cardiac output via the Fick or thermodilution methods, will be assessed by Right Heart Catheterization (RHC). For those subjects who consent to this assessment, the RHC procedure will be performed at the Baseline Visit (or within 0-21 days prior) and at the Month 6 Quarterly Visit (or within 7 days before or after).

An optional plasma concentration assessment will also be offered to subjects at study sites that are capable of collecting, processing and storing samples, are approved by the Sponsor and agree to participate. For subjects electing to participate, a trough (15 minutes pre-dose, \pm 5 minutes) blood sample will be collected at the Week 4 Visit and four blood samples will be collected during Week 12 (first Quarterly Visit) around the second daily dose of study drug (15 minutes pre-dose, and 15 minutes, 1 hour and 2.5 hours post-dose; \pm 5 minutes). If feasible, a sample should be collected for SAEs. Unwillingness to participate in the hemodynamic and/or the plasma concentration assessment sub-studies will not affect the subject's or site's participation in the main study.

Subjects will continue participation in the study until it is formally concluded by the Sponsor. When the Sponsor concludes the study the subjects will return to the study site for an End of Study visit to undergo all scheduled assessments. Subjects who are participating in the study at its conclusion may be offered the opportunity to enroll in a long-term open-label extension study.

In the event that a subject withdraws consent for participation in the study or the Investigator terminates the subject prior to formal study conclusion, the subject will be weaned from study drug and return to the study site for an End of Study Visit to undergo all scheduled assessments.

Study Population: 240 subjects are planned across sites in the U.S. and Israel.

Test Product, Dose, and Mode of Administration:

Beraprost sodium 314*d* Modified Release (BPS-314*d*-MR) tablets, 15 μ g for oral, four times daily (QID) administration. Subjects will begin treatment at a dose of 15 μ g QID. The dose will be increased by 15 μ g QID for a maximum dose of 30 μ g QID, 120 μ g total daily dose (TDD) as tolerated.

Duration of Treatment:

The maximum duration of treatment for an individual subject is expected to be 3 years. The anticipated date for last subject, last study visit in mid-2016.

Efficacy Assessments:

Efficacy parameters for this study include: clinical worsening, clinical failure, exercise capacity measured by a 6MWT, Borg Dyspnea Score, WHO Functional Class and NT-pro-BNP.

Safety Assessments:

Safety assessments will include the recording of adverse events (AE), clinical laboratory evaluations, ECG findings, physical examination, and vital signs.

Statistical Methods:

The primary efficacy endpoint is clinical worsening confirmed by an independent EAC. The primary efficacy endpoint analysis will evaluate clinical worsening as the time to first clinical worsening (TtCW) event.

Based on the assumptions specified in Section 10.2, a one-year rate of clinical worsening of 45% in the placebo (inhaled treprostinil alone) group, 25% in the BPS-314*d*-MR group (a 20% reduction from treprostinil, inhaled (Tyvaso®) therapy alone), proportional hazards over time, an accrual period of 1.5 years, a 0.01 two-sided significance level, and a total follow-up time of 2.5 years, an exponential maximum likelihood test of equality of survival curves would require 113 events and 116 subjects per treatment group to detect treatment difference at a power of 90% at a 0.01 two-sided significance level (or 97% power at a 0.05 two-sided significance level to detect a 13% reduction from an inhaled treprostinil rate as low as 30%). Therefore, this study will randomize approximately 240 subjects. Sample size calculations were performed using nQuery Advisor 7.0 using sample size methods for the log-rank statistic based on Lakatos & Lan (1992).

The Sponsor will continuously monitor the overall (pooled) event and drop-out rates during the course of the study. Sample size may be increased during the trial to maintain the planned power at between 80% and 90% and the intended trial duration. Only pooled blinded data will be used to increase sample size.

Date of Original Approved Protocol: 16 April 2013

Amendment 1: 17 December 2013

Amendment 2: 15 October 2014

TABLE OF CONTENTS

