4.3 Study Duration and Dates

As the trial is intended to continue until the specified number of Clinical Worsening Events (113) has occurred, the duration of treatment for individual subjects will vary. The maximum duration of treatment for any individual subject is expected to be 3 years, with the anticipated date for last subject last study visit in Q2 2016.

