Initial start-up activities and recruitment of subjects will be restricted to ensure subject safety. As such, the sample size determination calculations will not include the initial 6 months of the study to make certain of adequate powering for this study. The accrual period and follow-up period used will be 1.5 and 2.5 years, respectively. Thus, assuming a one-year rate of clinical worsening of 45% in the placebo (inhaled treprostinil alone) group, 25% in the BPS-314*d*-MR group (a 20% reduction from inhaled treprostinil therapy alone), proportional hazards over time, an accrual period of 1.5 years, a 0.01 two-sided significance level, and a total follow-up time of 2.5 years, an exponential maximum likelihood test of equality of survival curves would require 113 events and 116 subjects per treatment group to detect treatment difference at a power of 90% at a 0.01 two-sided significance level (or 97% power at a 0.05 two-sided significance level or approximately 90% power at a 0.05 two-sided significance level to detect a 13% reduction from an inhaled treprostinil rate as low as 30%). Therefore, this study will randomize approximately 240 subjects. Sample size calculations were performed using nQuery Advisor 7.0 using sample size methods for the log-rank statistic based on Lakatos & Lan (1992). Subjects who discontinue from the trial will not be replaced.

The Sponsor will continuously monitor the overall (pooled) event and drop-out rates during the course of the study. Sample size may be increased during the trial to maintain the planned power at between 80% and 90% and the intended trial duration. Only pooled blinded data will be used to increase sample size.

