Using the aforementioned published literature, the sponsor anticipates the one-year rate of clinical worsening will be approximately 15% for the population treated with inhaled treprostinil. As such, the sponsor considers the sample size necessary to show a clinically meaningful difference between the esuberaprost and the placebo groups treated with inhaled treprostinil to be prohibitively large. The sponsor intends to restrict recruitment to inhaled treprostinil subjects where an esuberaprost treatment effect will be more readily discerned. Following guidance from the Food and Drug Administration in 2012 (UCM332181) on clinical study enrichment strategies, the inclusion criteria of the current study (protocol, Section 5.2) specified that patients will be randomized into this study only if they are showing signs of deterioration after initial improvement on inhaled treprostinil treatment or have had a clinically suboptimal response to inhaled treprostinil treatment. The specific exclusion of subjects who are likely to be at a lower risk of clinical worsening will reduce the proportion of subjects available for recruitment; however, the targeted study population of those who have shown suboptimal response will be expected to have a higher event rate than would a broader population. Therefore, fewer subjects will be needed to test the hypothesized absolute effect size. Moreover, the target study population is one most likely to benefit from an additional therapy; without additional treatment, approximately 45% of these patients are expected to experience clinical worsening in a year.

Initial start-up activities and recruitment are restricted to ensure the safety of subjects. Therefore, the sample size calculations do not include the initial 6 months of the study to make certain the study has adequate power. The sample size calculations were based on the following assumptions:

- a one-year clinical worsening rate of:
 - 45% in the placebo group (inhaled treprostinil alone)
 - 25% in the esuberaprost group
- proportional hazards over time
- an accrual period of 1.5 years
- total follow-up time of 2.5 years (follow-up time for last subject randomized 1 year; total study duration 2.5 years)
- 0.01 two-sided significance level

[figure not shown]

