This study will randomize approximately 240 subjects (120 subjects per treatment group). Calculation of the sample size was based on the assumptions listed above. Under those assumptions, an exponential maximum likelihood test of equality of survival curves would require 113 events overall to detect a treatment difference at a power of 90% at a 0.01 two-sided significance level. Given the expected accrual period and follow-up time, an appropriate sample size is 240 subjects. There was no restriction or quota with respect to number of subjects by country.

Study sample size is based on a 0.01 two-sided significance level to provide sufficient power to observe ‘substantial evidence’ of effectiveness within a single clinical study. However, at the time of the analysis, the effect will be tested at a significance level of 0.05 (see Section 6.10). The power at a 0.05 two-sided significance level is 97%.

Sample size calculations were performed with nQuery Advisor 7.0 (2014) and PASS (Hintze, 2013) using sample size methods for the log-rank statistic based on Lakatos & Lan (1992).

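### The Synopsis claims 97% power for 30% vs 17%; that figure belongs to 45% vs 25%, and the 90% in Section 10.2 holds only if the trial runs past 2.5 years

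*Protocol*

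**What the plan says.** - **Protocol Synopsis, Statistical Methods.** After the main calculation, a bracket gives "97% power at a 0.05 two-sided significance level to detect a 13% reduction from an inhaled treprostinil rate as low as 30" per cent. The paragraph says it rests on the assumptions of Section 10.2.
- **Protocol Section 10.2.** The corresponding bracket holds two items: 97% power at 0.05, and then "approximately 90% power at a 0.05 two-sided significance level to detect a 13% reduction from an inhaled treprostinil rate as low as 30" per cent. The sentence takes "a one-year rate of clinical worsening of 45% in the placebo (inhaled treprostinil alone) group", 25% in the active group, 1.5 years of accrual and 2.5 years of total follow-up. It arrives at 113 events and 116 subjects per group for "a power of 90% at a 0.01 two-sided significance level".
- **SAP Section 4.1.** The only rates given are 45% for placebo and "25% in the esuberaprost group". It explains that "at the time of the analysis, the effect will be tested at a significance level of 0.05", and adds: "The power at a 0.05 two-sided significance level is 97" per cent. The 30% scenario does not appear.
- **Protocol Section 4.3.** The stopping rule is event-driven: "the trial is intended to continue until the specified number of Clinical Worsening Events (113) has occurred". The same section expects no subject to be treated for more than 3 years.

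**The concern.** The protocol gives two powers, 97% and about 90%, for one scenario at one significance level. They cannot both be right.

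The scenario is the plan's robustness statement. Section 10.2 puts the literature-based one-year rate at about 15% and reaches 45% only through enrichment, so a placebo rate below 45% is the foreseeable risk. The Synopsis says the trial would keep 97% power if that rate were 30%.

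A second question is whether 90% itself holds. The Section 10.2 sentence fixes total follow-up at 2.5 years, while Section 4.3 runs the trial to 113 events. With lower rates these two bases no longer give similar answers, and the sentence does not choose between them.

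**Working it through.** **Inputs.** One-year rates, 1.5 years of accrual, 2.5 years in total, and 116 or 120 subjects per group come from Protocol Section 10.2 and SAP Section 4.1. The 13% reduction is read as percentage points, because Section 10.2 calls 45% to 25% a 20% reduction; the scenario is therefore 30% vs 17%. Accrual is taken as uniform. The documents give no dropout rate, so none is assumed at first.

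**Formulas.**
- Hazard from a one-year rate r: λ = −ln(1 − r).
- Probability of an event with accrual A and total time T: p(λ) = 1 − [exp(−λ(T − A)) − exp(−λT)]/(λA).
- Exponential maximum likelihood (ML) test, n per group, λ̄ the mean hazard: power = Φ{[√n·|λ₁ − λ₂| − z·√V₀]/√V₁}, where V₀ = 2λ̄²/p(λ̄) and V₁ = λ₁²/p(λ₁) + λ₂²/p(λ₂).
- Log-rank with d events: Schoenfeld, Φ(½√d·|ln HR| − z); Freedman, Φ(√d·(1 − HR)/(1 + HR) − z).

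**Step 1: reproduce the plan (45% vs 25%).** λ = 0.598 and 0.288, HR 0.481, p = 0.637 and 0.391, V₀ = 0.739, V₁ = 0.773.
- At 0.01 and 90% power the ML test needs n = 116.0 per group, as stated. Schoenfeld needs 112 events, against 113 stated.
- At 0.05 with n = 116: (10.770 × 0.3102 − 1.960 × 0.8595)/0.8792 = 1.88, so power is 97.0%.

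The stated 97% is therefore the power for 45% vs 25%.

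**Step 2: 30% vs 17%, study closed at 2.5 years.** λ = 0.357 and 0.186, HR 0.522, p = 0.458 and 0.276, V₀ = 0.394, V₁ = 0.404.
- Expected events: 116 × (0.458 + 0.276) = 85, or 88 with 120 per group.
- ML, n = 120: (10.954 × 0.1703 − 1.960 × 0.6279)/0.6354 = 1.00, so power is 84.1%.

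| Power at two-sided 0.05, 2.5 years | 116 per group | 120 per group |
|---|---|---|
| Exponential ML | 82.9% | 84.1% |
| Schoenfeld | 85.0% | 86.1% |
| Freedman | 82.5% | 83.7% |
| Log-rank, 20,000 simulated trials | 84.1% | 85.0% |

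**Step 3: 30% vs 17%, study run to 113 events.**
- Schoenfeld: ½ × √113 × 0.6493 − 1.960 = 1.491, power 93.2%.
- Freedman: √113 × 0.4776/1.5224 − 1.960 = 1.375, power 91.5%.
- ML 91.8%; simulated log-rank 92.8% to 92.9%.
- 113 events are expected at 3.3 years (116 per group) or 3.2 years (120 per group). This clock leaves out the first 6 months, as Section 10.2 does.

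**Step 4: events needed for the stated powers.**
- 90%: 100 (Schoenfeld) to 107 (Freedman), reached at about 2.8 to 3.1 years.
- 97%: 4 × (1.960 + 1.881)²/0.6493² = 140 (Schoenfeld), or 150 (Freedman). Both exceed the 113 target.

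**Step 5: dropout (an assumption).** With 120 per group and 5%, 10% or 20% dropout per year, ML power at 2.5 years is 82.6%, 81.0% or 77.3%. Power at 113 events stays near 92%, but reaching them takes 3.4, 3.7 or 5.1 years.

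**Step 6: other readings.**
- Taking 13% as relative (30% to 26.1%, HR 0.848) gives about 14% power at 113 events.
- Taking 2.5 years as time after accrual closes (4 years in total) gives 95% to 97% for 30% vs 17%. The base design would then have about 169 events and about 98% power at 0.01, against the stated 113 and 90%. SAP Section 4.1 also defines 2.5 years as the total study duration.

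**The case against.** The Synopsis error is a dropped clause, and the full sentence stands in Section 10.2, to which the Synopsis points. SAP Section 1 says that the SAP supersedes the protocol's statistical considerations; the SAP ties 97% to the right rates and omits the 30% scenario. Nothing in the conduct or analysis of the trial rests on the misplaced figure. All of this is correct, and it limits the consequence to a stated number.

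The stronger objection concerns Section 10.2. The trial stops at 113 events, where power is 91.5% to 93.2%, so about 90% is fair and even slightly cautious; closing at 2.5 years is not the stopping rule. Section 10.2 also allows a blinded increase in sample size to hold power between 80% and 90%, and the no-dropout figures at 2.5 years lie inside that range. This stands as far as it goes: the 90% is not an arithmetic error.

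It does not remove the need to name the basis. The sentence cites 2.5 years and no other duration. Under 30% vs 17% with 240 subjects, 113 events take about 3.2 years on a clock that omits the first 6 months, while Section 4.3 expects at most 3 years of treatment for any subject. A reader cannot tell which of these the 90% assumes.

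**Conclusion.** The concern holds. The Synopsis figure is wrong for the scenario it names: 97% is the power for 45% vs 25%. For 30% vs 17% the power is 91.5% to 93.2% at 113 events, or 82.5% to 86.1% at 2.5 years. The implied type II error of 3% is really about 7% to 8.5%, or about 14% to 17.5% if the study closes at 2.5 years. The 90% in Section 10.2 is sound under the event-driven rule, but its sentence leaves out that condition.

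These results assume exponential event times, uniform accrual, 1:1 allocation, an absolute 13-point reduction and no dropout. Dropout would lower the 2.5-year power and lengthen the wait for 113 events. The case for change is a wrong headline power in the Synopsis that costs little to correct.

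**What to change.** 1. **Synopsis.** Attach 97% at two-sided 0.05 to 45% vs 25%, by restoring the separation of the two figures found in Section 10.2.
2. **Synopsis and Section 10.2.** Give the second scenario with its basis, for example: *for one-year rates of 30% vs 17% (an absolute reduction of 13 percentage points, no dropout assumed), power at two-sided 0.05 is about 92–93% at 113 events, expected at about 3.2 years with 240 subjects, or about 84–86% with 240 subjects if the study closes at 2.5 years.* If a shorter text is preferred, keep the approximate 90% and add that it applies at 113 events.

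The cost is a text correction in two places. The Synopsis figure becomes less favourable; the Section 10.2 figure can stay once its basis is given. Enrolment, the 113-event target, the test and alpha do not change.
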